2.4. Outcome Measures

Participants completed self-reported symptom severity measures every evening during the study, using the Qualtrics Research Suite (Qualtrics, Provo, UT, USA) on a tablet. The primary

outcome used in this clinical trial was a 0–100 item assessing overall GWI severity. The item read, "Overall, how severe have your symptoms been today?" The zero response was anchored by "No symptoms at all" and 100 was labelled as "Severe symptoms". This generic symptom response was chosen because GWI sufferers can have a wide range of principal complaints.

2.5. Secondary Outcome Measures

To further explore the impact of botanicals on common GWI complaints, we also measured changes in pain and fatigue severity. Both outcomes were measured on a 0–100 scale. Pain was measured by the item, "Overall how severe is your pain?" from "No pain at all" to "Severe pain". Fatigue was measured by "How fatigued have you felt today?" from "Not fatigued at all" to "Severely fatigued". Other GWI symptom domains such as respiratory and skin issues were rarely endorsed by participants and were not analyzed.

2.6. Statistical Analyses

All analyses were conducted in SPSS version 24 (IBM Corp., Armonk, NY, USA). For each botanical, a linear mixed model (LMM) was created to test changes in the primary outcome. LMMs were used to accommodate the repeated outcome assessments in each condition, nested in each participant. Subject ID was the repeated-measures nesting variable, the repeated-measures index was the day in the study, and the repeated measures covariance type was compound symmetry. The predictor was study condition, which could take four values (baseline, placebo, lower-dose, and higher dose botanical). The last 14 days of each condition were included in the models. The final 14 days of the baseline condition at the beginning of participation were used as the baseline for all tested botanicals. Post hoc tests were conducted using least-squares differences. A p < 0.05 was used for all tests. The same statistical approach was used to test the secondary outcomes of pain and fatigue. Nine total models are presented in this report (three botanicals tested for the outcomes of GWI severity, pain and fatigue).

If a participant did not complete the protocol, any valid data were still used in statistical tests. However, data imputation of missing values was not used, and participants were not included if they never took the assigned botanical. Therefore, we did not use a complete intent-to-treat method for analysis.

The three trials were powered to detect within-person fixed effects for study condition (baseline, placebo, lower dosage and higher dosage). Detection of a medium effect size (Cohen's d = 0.5) was targeted at a threshold of p < 0.05. With 56 repeated outcome assessments per participant, and a repeated measures correlation of 0.5, it would require 10 individuals to achieve 0.99 power for the main effect test.

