2.7. Statistical Analyses

SPSS Statistics for Windows, version 24 (IBM Corp., Armonk, NY, USA) was used to conduct analyses. Linear mixed models (LMM) were utilized to test differences in self-reported symptom severity between the four conditions. A separate model was tested for each of the three botanicals. Subject ID was entered as the subject identifier, with all individual longitudinal data nested within-person. The participant's day in the study was entered as the index variable for repeated measures. Compound symmetry was selected as the repeated measures covariance type. The AR (1) autoregressive covariance type was also considered, but it did not improve the Akaike information criterion (AIC) or Bayesian information criterion (BIC) for model performance. The dependent variable was daily GWI symptom severity (0–100). Treatment condition (baseline,

placebo, lower-dose, and higher-dose) was entered as a fixed factor. The last 14 days of each condition were selected for analyses to permit time for clinical effects of the treatments to occur. A restricted maximum likelihood (REML) estimation approach was used. Statistical significance was set at p < 0.05 for all tests. The secondary analyses were conducted using the same approach.

We performed a-priori power analyses using G*Power 3 [43] to estimate sample size. Each of the nine botanical trials was powered to detect a medium effect (Cohen's d = 0.5) at 0.99 power with p = 0.05 threshold for significance. Given 56 repeated outcome measurements per participant (with a repeated measures correlation of 0.5), each trial required 10 individuals to obtain 0.99 power. Our studies were not powered (0.42 predicted power) to detect small effects (Cohen's d = 0.25).

A Placebo-Controlled, Pseudo-Randomized, Crossover Trial of Botanical Agents for Gulf War Illness: Reishi Mushroom (Ganoderma lucidum), Stinging Nettle (Urtica dioica), and Epimedium (Epimedium sagittatum)

2. Materials and Methods

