2.3. Study Protocol

Individuals were screened via an online questionnaire and phone interview, followed by an in-person screening conducted at UAB's Clinical Research Unit (CRU). Informed consent was obtained at the in-person visit, and blood samples were collected for further screening. As the screening involved blood tests, individuals provided informed consent before being determined eligible for participation. Therefore, several individuals who provided consent were not eligible to participate in the study. Consented individuals received a tablet device for completing daily symptom reports each evening for the duration of their study participation.

Before beginning capsules, all participants completed a baseline period of 30 days. This period served as the baseline for all botanicals taken by the participant. Participants then were pseudo-randomized to receive up to three of the nine study compounds, as seen in **Figure 1**. A pseudo-randomized procedure was used to avoid contraindications with the botanicals. Randomization was conducted by a pharmacist. The pharmacist in charge of blinding and randomization was not otherwise involved in the study. The research personnel were blinded to the botanicals assigned to each participant. For each botanical, participants completed 30 days of placebo capsules, 30 days of lower-dose botanical, and 30 days of higher-dose botanical. Participants were blinded to all aspects of the study (the protocol and botanicals assigned). Research personnel were blinded to the botanicals assigned, though they were aware that placebo occurred first, followed by lower-dose and higher-dose treatment.

[figure not shown]

Figure 1. Study event flow. Participants took three of the tested compounds in the following order: placebo, lower-dose botanical, and higher-dose botanical.

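### If daily scores were modelled, compound symmetry on subject alone ignores month-level and day-to-day correlation, so the condition tests are not assured a 5% error rate

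*Combined protocol and SAP*

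**What the plan says.** The combined document holds three reports, each with its own statistical section.

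- **Reishi/nettle/epimedium, section 2.6.** The reason given for a mixed model is that "LMMs were used to accommodate the repeated outcome assessments in each condition, nested in each participant". In the model itself subject ID is the only nesting variable, and "the repeated-measures index was the day in the study, and the repeated measures covariance type was compound symmetry". On the rows: "The last 14 days of each condition were included in the models". On the baseline: "The final 14 days of the baseline condition at the beginning of participation were used as the baseline for all tested botanicals". Incomplete participants are kept, since "any valid data were still used in statistical tests". The power statement begins "With 56 repeated outcome assessments per participant". No daily dependent variable is named, but the day index, the 14-day window and 56 = 4 x 14 all point to daily rows.
- **Resveratrol/luteolin/fisetin, section 2.7.** The dependent variable is stated to be the daily score. "Subject ID was entered as the subject identifier, with all individual longitudinal data nested within-person". Compound symmetry was chosen because AR(1) did not improve AIC or BIC.
- **Curcumin/boswellia/maritime pine, section 2.7.** The data are described as nested in both individuals and conditions. The section says that daily severity was the dependent variable, and also that the outcome in all analyses was a 14-day mean per condition. Compound symmetry was again preferred to AR(1).

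No section describes a subject-by-condition term, a subject effect combined with serial correlation, a robust standard error or a degrees-of-freedom method. The only correlation given is the planning value of 0.5.

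**The concern.** Treatment changes once a month: "For each botanical, participants completed 30 days of placebo capsules, 30 days of lower-dose botanical, and 30 days of higher-dose botanical". A person's 14 evenings in one month share whatever made that month good or bad, and successive evenings may resemble each other. Compound symmetry on subject has no term for either. Because the first baseline serves every botanical, the model gives a baseline evening and a higher-dose evening of the third botanical the same correlation as two consecutive evenings.

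If daily rows were used and the omitted correlation is positive, the model treats the 14 days as carrying more independent information about a condition than they do. Standard errors come out too small, and a botanical or dose is declared effective by chance more often than 5% of the time. The same approach is used for overall severity, pain and fatigue. The least-squares-difference contrasts inherit the same error term.

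**Working it through.** **The plan's own figure.** Inputs from the power paragraphs: N = 10, m = 56, correlation 0.5, d = 0.5 (f = d/2 = 0.25), alpha 0.05. With lambda = N·m·f²/(1 − rho) = 10 × 56 × 0.0625/0.5 = 70 and df 55 and 495, power is 0.997 (stated 0.99). For d = 0.25, lambda = 17.5 and power is 0.417 (stated 0.42). The figures reproduce, but as a test among 56 exchangeable days with 55 numerator df. The condition test has 3.

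**Degrees of freedom.** The documents give none; these follow from 10 complete participants.

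- Daily rows: 560 − 10 subjects − 3 conditions = 547 error df.
- These split into subject-by-condition, 9 × 3 = 27, and days within condition, 10 × 4 × 13 = 520.

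**Mean squares.** Let p be the month-level share of within-person variance (assumed; not in the documents), with within-person variance set to 1.

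- Expected mean square for condition, no true effect: (1 − p) + 14p = 1 + 13p.
- Expected pooled residual: [27(1 + 13p) + 520(1 − p)]/547.
- True SE over model SE: the square root of their ratio. At p = 5% this is √(1.65/0.985) = 1.29.

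**Error rates by simulation, no true effect, n = 10:**

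| Share p | True SE / model SE | Four-condition test | One contrast |
|---|---|---|---|
| 0 | 1.00 | 5% | 5% |
| 0.5% | 1.03 | 6% | 6% |
| 1% | 1.06 | 7.5% | 7% |
| 2% | 1.13 | 10% | 8% |
| 5% | 1.29 | 20% | 13% |
| 10% | 1.54 | 35% | 20% |
| 20% | 1.96 | 56% | 32% |

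At p = 5% the four-condition rate is also about 20% with 20 or 30 participants, because the variance ratio barely depends on n.

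**Other forms of omitted correlation (all assumed):**

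- Serial correlation alone of 0.1 or 0.2: four-condition error about 9% or 15%.
- Slow drift with a 30-day half-life. On 30-day months the baseline window is days 17–30 and the third botanical's higher-dose window is days 287–300, so the largest gap is 283 days. A 5% share gives about 12% for a first and 15% for a third botanical. A 10% share gives 21.5–23% for a first (two simulations) and about 26% for a third.
- With 15% of daily reports and 20% of higher-dose months missing, a 5% share gives 17% (four-condition) and 12% (one contrast).

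**Comparison.** Testing condition against subject-by-condition means (3 and 27 df) held 4.8–5.3% across balanced settings with month shares up to 30% and serial correlation up to 0.5. Paired contrasts on 14-day means, with equal or unequal report counts, held 3.7–5.9%.

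**Power in the right stratum.** Take higher dose 0.5 total SD above placebo, lower dose midway, baseline equal to placebo, person correlation 0.5. The squared deviations sum to 0.1719. The variance of a condition mean is 0.5[p + (1 − p)/14], and lambda = 10 × 0.1719 divided by that variance. At p = 0/5/10/20%, lambda is 48.1/29.2/20.9/13.4, and power on 3 and 27 df is 1.00/0.99/0.96/0.825. Adding serial correlation of 0.2 gives 0.92 at 10% and 0.78 at 20%. If f = 0.25 and correlation 0.5 were meant for the four condition means themselves, lambda = 10 × 4 × 0.0625/0.5 = 5 and power is 0.39.

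**The case against.** **Daily rows are not certain.** The curcumin/boswellia/pine report says the outcome in all analyses was a 14-day mean and describes this as consistent with the registered plan, which all three reports share. On means the problem disappears. This stands as a condition on the finding. However, that sentence may refer only to the 14-day window, the same section says daily severity was entered, and the resveratrol/luteolin/fisetin report states a daily outcome outright.

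**The covariance structure was checked.** Two reports preferred compound symmetry to AR(1). This argues against strong serial correlation: at a neighbouring-day correlation of 0.5, compound symmetry won in only 0–12% of simulated trials. It does not exclude milder correlation, since at 0.3 it won in about 90–98%. Nor does it test for month-level variance, which neither model contains: with a 10% or 20% month share, compound symmetry won in all 60 trials. The reishi/nettle/epimedium report gives no comparison.

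**The size is assumed.** This is true. The defect is an unverified assumption, not a demonstrated error in this trial's results.

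**A rerun does not rescue the inference.** Condition remains confounded with the fixed month order. That is a separate limitation, and it does not make a wrong error term acceptable.

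**Conclusion.** The concern holds, conditional on daily rows. Those are stated for resveratrol/luteolin/fisetin, implied for reishi/nettle/epimedium, and contradicted within the curcumin/boswellia/pine report. Where they were used, the tests keep 5% error only if same-month and neighbouring days carry no extra correlation. The documents give no figure from which to judge this, so the excess could be negligible or large. A month-level share of about 1.9% is enough to double the four-condition error to 10%. All rates rest on assumed variance components and, except where missing data are mentioned, on 10 complete participants. This should be fixed. Confidence is medium: the missing model term is clear, its effect on these results is not.

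**What to change.** Reconcile the two outcome definitions in the curcumin/boswellia/pine report and state one outcome unit for all three reports. Then rerun with one of:

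- **(a) Means.** One 14-day mean per participant per condition, including baseline, with a subject effect, small-sample df and contrast-specific (paired) errors, allowing for unequal numbers of reports per mean.
- **(b) Daily rows.** A random subject-by-condition effect with Satterthwaite or Kenward-Roger df, and within-condition AR(1) as a sensitivity analysis. Over shares of 0–20% and serial correlation of 0–0.3, simulated error was 2.2–5.8% for the four-condition test and 3.0–5.7% for a contrast. Under slow drift, the higher-dose versus baseline contrast with a pooled error reached about 6–8%, while paired contrasts held about 5%, so contrast-specific errors are advisable here too.

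Report the subject-by-condition variance and the serial correlation. If both are near zero, the existing p-values stand. Describe the 0.99 power as conditional on exchangeable days.

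The cost is a rerun on existing data, with wider intervals if the omitted variance is not zero. Where it is zero, option (b) is somewhat conservative (four-condition error 2–4%). In the scenario above without serial correlation, power stays at 0.96 or more up to a 10% share.

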2.3. Study Protocol

All participants were assessed for initial eligibility for the study using an online prescreening questionnaire, followed by a phone interview. Individuals who met initial inclusion criteria after the online screening and phone interview were given an in-person screening at UAB's Center for Clinical and Translational Science Clinical Research Unit (CCTS CRU).

At the in-person screening visit, participants provided written informed consent as well as blood samples to test for exclusionary lab values. Participants also completed baseline study measures on a tablet device and were loaned a tablet for completion of daily symptom reporting during the study. Following the screening visit, participants reported symptoms every day (in the evening) during a one-month (30 + /- 3 days) baseline period, which served as a habituation period and a means to assess whether participants would reliably complete their daily symptom reports. Participants were allowed to continue with study participation if they completed at least 80% of baseline symptom reports.

Participants were then pseudo-randomized to receive up to three out of the nine botanical compounds, in the design presented in Figure 1. Botanical assignments were pseudo-randomized so that (1) approximately equal numbers of participants would take each botanical and (2) to ensure there were no drug interactions that contraindicated the use of the botanicals assigned to participants. There were no contraindications used for curcumin or boswellia. Individuals with prediabetes, evidence of diabetes, or diabetic medications were excluded from taking maritime pine due to its lowering effects on blood glucose [40]. Contraindications were handled by a pharmacist with no other connections to the study so that all research personnel could remain blinded to the botanical being assigned. After completion of a full protocol of three botanical assignments, participants were offered the opportunity to re-enroll into the study protocol to receive up to three more botanicals.

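### No dose-versus-placebo comparison is formally named or powered; the one powered test is a four-condition main effect that a baseline-only difference can make significant

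*Combined protocol and SAP*

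**What the plan says.** The file contains three reports, called here the curcumin, resveratrol and reishi reports after the first agent in each title.

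- **Model.** All three analysis sections (curcumin 2.7, resveratrol 2.7, reishi 2.6) fit a mixed model with condition as a four-level fixed factor that includes baseline. The resveratrol report puts the aim as to "test differences in self-reported symptom severity between the four conditions".
- **Baseline.** It is a month before any capsules. The reishi report (2.3) says "This period served as the baseline for all botanicals taken by the participant", and its 2.6 repeats this for the analysis: "The final 14 days of the baseline condition at the beginning of participation were used as the baseline for all tested botanicals". The curcumin report (2.3) describes the same month as one "which served as a habituation period and a means to assess whether participants would reliably complete their daily symptom reports".
- **Order.** Within each botanical, "placebo occurred first, followed by lower-dose and higher-dose treatment" (reishi 2.3).
- **Contrasts.** The reishi report says "Post hoc tests were conducted using least-squares differences". The curcumin report also uses least-squares differences (LSD). Neither singles out a pair. The resveratrol report specifies no contrasts.
- **Power.** Reishi 2.6: "The three trials were powered to detect within-person fixed effects for study condition (baseline, placebo, lower dosage and higher dosage", and with 56 assessments per participant, correlation 0.5 and d = 0.5, "it would require 10 individuals to achieve 0.99 power for the main effect test". The other two reports give the same 0.99 with 10 participants, add 0.42 at d = 0.25, and name no contrast.
- **Unit of analysis.** Curcumin 2.7 says that daily severity was the dependent variable. It also says that the outcome was a mean over the last 14 days, listed for three conditions although its model has four. The other two reports read as daily rows.

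**The concern.** A placebo-controlled trial asks whether a dose differs from placebo. The test to which the reishi report ties its power asks something wider: whether any of four conditions differ, one of them a month with no capsules. At first enrolment baseline is month 1 and the placebo months are 2, 5 and 8, so baseline precedes its placebo month by 1, 4 or 7 months. Placebo response, habituation to daily rating, or drift could each separate baseline from all the capsule months. Any of these can make the main effect, or a dose-versus-baseline contrast, significant with no botanical effect at all.

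A shift in baseline does not bias dose versus placebo. The difficulty is that the documents do not formally make that comparison the deciding one, do not control error over the two doses, and attach their power to something else.

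**Working it through.** **Inputs from the documents:** n = 10, 56 assessments (4 conditions × 14 days), correlation 0.5, alpha 0.05, d = 0.5 and 0.25. **Assumptions:** f = d/2; total variance 1, of which 0.5 is between participants; size of the baseline shift; share of participant-by-condition variance. The documents give no SD and no size of placebo response.

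**1. The stated power.** With 56 days as 56 levels, lambda = f² × 10 × 56 / (1 − 0.5), df 55 and 495.
- d = 0.5: 0.0625 × 560 / 0.5 = 70, power 0.997 (stated 0.99).
- d = 0.25: 0.015625 × 560 / 0.5 = 17.5, power 0.417 (stated 0.42).

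Both figures reproduce, but the condition factor has 3 df. On the same inputs:
- 3 df, daily rows (df 3 and 547, same lambda): >0.999 and 0.95.
- 3 df, four means per participant (lambda = f² × 40 / 0.5 = 5 and 1.25, df 3 and 27): 0.39 and 0.12.

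**2. Baseline-only difference.** Placebo and both doses are equal and baseline is shifted by d, so f² = 3d²/16 (0.0075 at d = 0.2). At d = 0.2:
- Daily rows, pure compound symmetry: lambda = 560 × 0.0075 / 0.5 = 8.4, df 3 and 547.
- 14-day means, 10% participant-by-condition variance: lambda = 40 × 0.0075 / (0.1 + 0.4/14) = 2.33, df 3 and 27.
- Shift and correlation defined on the means: lambda = 40 × 0.0075 / 0.5 = 0.6, df 3 and 27.

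| Rejection by the four-level test | 0.2 SD | 0.3 SD | 0.5 SD |
|---|---|---|---|
| Daily rows, pure compound symmetry | 67% | 97% | >99.9% |
| 14-day means, 10% participant-by-condition | 19% | 40% | 86% |
| Shift and correlation on the means | 8% | 13% | 30% |

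In simulation of the first row at 0.5 SD, 90.8% of trials had a significant main effect with neither dose differing from placebo.

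**3. Dose versus placebo under no effect (simulation).** Each LSD contrast rejects at 5% whatever baseline does (pure compound symmetry). At least one of the two rejects in about 9%, and in about 4% if they are gated on a 2-df test of placebo, lower and higher dose.

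**4. Unit of analysis, no effect (simulation).** The 2-df test on daily rows with compound symmetry alone rejects 5%, 29% and 46% at 0, 5% and 10% participant-by-condition variance. On 14-day means it rejects 5% at each. The four-level test on daily rows at 10% rejects 56% with no baseline shift and about 80% with 0.2 SD.

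**The case against.** The strongest reply is that the placebo comparison is plainly intended. All three titles call the trial placebo-controlled, every botanical has its own placebo month, and the LSD tests of two reports include dose versus placebo, which a baseline shift leaves unbiased. This stands. A reader might infer that the trial has no placebo comparison, or that nothing points to one. The documents do not support that: the comparison exists but is not formally named, ranked or powered.

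The curcumin report also cites a registered analysis plan that is not in the file and may name the contrast. The point is therefore limited to these documents, and it does not follow that no such comparison was prespecified.

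The size of the effect rests on assumptions and runs from 8% to over 99.9%. That is fair. The structural point needs no particular shift, but no single percentage should be quoted as the trial's error rate. The daily index and the 56 assessments per participant suggest daily rows, where step 4 shows that the error structure can do more harm than the baseline. Removing baseline is therefore not enough.

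Finally, a 2-df test is not itself a dose-versus-placebo contrast. A difference between the doses, or drift, can make it significant. It is only one way to control multiplicity.

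**Conclusion.** The point holds in this limited form. The documents name a primary outcome but do not formally name or power a dose-versus-placebo comparison. The only powered test includes a reused capsule-free baseline and can be significant with placebo and both doses identical: 67%, 19% or 8% at an assumed 0.2 SD shift, depending on the unit and variance assumed. The printed 0.99 and 0.42 are correct arithmetic for a 55-df test across days. They are the power of neither the 3-df condition test nor a dose-versus-placebo comparison. Curcumin 2.7 contradicts itself on what was analysed, and the choice matters: power of the 3-df test at d = 0.5 is >0.999 on daily rows and 0.39 on four means.

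A reader might go on to infer that reported botanical effects are baseline artefacts. These sections contain no results, so that cannot be said. This should be fixed; confidence is medium because the size depends on assumed values and the registered plan was not seen.

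**What to change.** In all three analysis sections:

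1. Name dose versus placebo, within that botanical's own cycle and on overall GWI severity, as the efficacy comparison. Control multiplicity over the two doses; a 2-df gate on placebo, lower and higher dose is one option, Holm another.
2. Keep baseline descriptive. Base no efficacy claim on the four-level main effect or on dose-versus-baseline contrasts.
3. Analyse one 14-day mean per participant per condition, as curcumin 2.7 already describes, or daily rows with a participant-by-condition random effect. Do not use daily rows with compound symmetry alone. Reconcile curcumin 2.7 with the other two reports.
4. Replace the stated power with that of the named comparison, giving the scale of d and the assumed variance.
5. The analyses are written in the past tense, so label the comparison post hoc unless the registered plan already names it.
6. State that the fixed order leaves time drift confounded with dose. With an assumed 0.1 SD per month and no effect, the 2-df test rejects 55% on daily rows (pure compound symmetry) and 16% on 14-day means with 10% participant-by-condition variance.

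The cost is a short paragraph per section, a re-run on existing data and a less favourable power. For the 2-df test at d = 0.5 with the lower dose halfway, the variance of the three means is 0.0417. On 14-day means with 10% participant-by-condition variance, lambda = 30 × 0.0417 / 0.1286 = 9.72 and power is 0.73. If d and the correlation are defined on the means, lambda = 30 × 0.0417 / 0.5 = 2.5 and power is 0.24 (df 2 and 18 in both).
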